Methods: *Describe in lay terms, completely detailing the research activities that will be conducted by Mayo Clinic staff under this protocol.*

The Papette and spatula/cytology brush for cervical cancer screening are currently both available for use in the primary care clinics (Community Internal Medicine and Family Medicine) and Obstetrics and Gynecology clinic at Mayo Rochester campus. However, providers in Community Internal Medicine would like additional data on the benefits of one collection method versus the other. Although, both methods of Pap smear collection are available this is not typically documented in the chart so a simple chart review study can not address the outcome.

Within Community Internal Medicine (CIM) we aim to complete 353 Pap smears using the Papette and 353 Pap smears using the traditional spatula/cytology brush from July 2021-June 2022. The total sample size will be 706 patients. Cluster sampling will be used: CIM practice in Rochester are located at Baldwin, NW, NE and SE clinics. The Baldwin practice is divided into 4 care teams: Ba5A, Ba5B, Ba6A and Ba6B. The Papette brush will be used to obtain Pap smear samples in women seen at CIM Ba5A, Ba5B and NW clinic while spatula/cytobrush will be used to obtain Pap smear samples at Ba6A, Ba6B, NE and SE clinics. Collection will be done until end of study date or until target sample size is met whichever comes first.

Outcome data to be collected:

-Demographics

-Cytology report on cellular adequacy: a retrospective review of subject medical record will be done to capture cytology report on completed Pap smear exam.

-Cervical bleeding with collection, ease of usage, time of collection, perceived pain, indication for pap smear, problem encountered: Provider who performed pap smear will be asked to complete a short questionnaire right after completion of exam.

Data will be stored in a secure database with only research members listed on the IRB having access to data.

Subject Information

Target accrual is the proposed total number of subjects to be included in this study at Mayo Clinic. A "Subject" may include medical records, images, or specimens generated at Mayo Clinic and/or received from external sources.

Target accrual: 706 Pap smear samples

Subject population (children, adults, groups): Adult women aged 21-64 years old eligible for pap smear exam; Providers performing Pap smear samples in CIM.

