Inclusion Criteria: Adult women aged 21-64 years old who gave consent for medical records to be accessed and who will have a Pap smear exam in CIM from July 2021 through June 2022; Providers performing Pap smear samples in CIM.

Exclusion Criteria: Women <21 or >64; has vaginal spotting present during cervical sampling; did not give consent to have medical records accessed; Providers not part of CIM.

Biospecimens

Collection of blood samples. When multiple groups are involved copy and paste the appropriate section below for example repeat section b when drawing blood from children and adults with cancer.

a. **From healthy, non-pregnant, adult subjects who weigh at least 110 pounds.** For a minimal risk application, the amount of blood drawn from these subjects may not exceed 550ml in an 8 week period and collection may not occur more frequently than 2 times per week.

Volume per blood draw: N/A ml

Frequency of blood draw (e.g. single draw, time(s) per week, per year, etc.) N/A

b. **From other adults and children considering age, weight, and health of subject.** For a minimal risk application, the amount of blood drawn from these subjects may not exceed the lesser of 50 ml or 3 ml per kg in an 8 week period, and collection may not occur more frequently than 2 times per week.

Volume per blood draw: N/A ml

Frequency of blood draw (e.g. single draw, time(s) per week, per year, etc.) N/A

Prospective collection of biological specimens other than blood: Pap smear sample

Review of medical records, images, specimens

Check all that apply (data includes medical records, images, specimens).

Only data that exists before the IRB submission date will be collected.

Date Range for Specimens and/or Review of Medical Records:

Examples: *01/01/1999 through 12/31/2015*, or all records through *mm/dd/yyyy*.

Note: The Date Range must include the period for collection of baseline data, as well as follow-up data, if applicable.

The study involves data that exist at the time of IRB submission **and** data that will be generated after IRB submission. Include this activity in the Methods section.

Examples

- The study plans to conduct a retrospective chart review and ask subjects to complete a questionnaire.
- The study plans to include subjects previously diagnosed with a specific disease and add newly diagnosed subjects in the future.

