The study will use data that have been collected under another IRB protocol. Include in the Methods section and enter the IRB number from which the research material will be obtained. *When appropriate, note when subjects have provided consent for future use of their data and/or specimens as described in this protocol.*

Enter one IRB number per line, add more lines as needed

Data Specimens Data & Specimens _____

Data Specimens Data & Specimens _____

Data Specimens Data & Specimens _____

Data Analysis

Power analyses may not be appropriate if this is a feasibility or pilot study, but end-point analysis plans are always appropriate even if only exploratory. Provide all information requested below or provide justification if not including all of the information.

Power Statement:

A total sample size of 706 women (353 per cluster) is needed to detect a difference of 0.2 between the means of the brushes with 80% power, a two-sided significance level of 0.05, and an intraclass correlation was 0.1.

Data Analysis Plan:

Descriptive statistics will be reported for patient demographics by type of procedure. Chi-square tests will be used for categorical variables and Kruskal-Wallis test for continuous variables. For the primary analysis, a linear mixed model will be used to model the impact of procedure type on the rate of inadequate endocervical cells. The model will include a fixed procedure effect and a random cluster effect. As a sensitivity analysis, covariates such as age, previous bleeding history, and other factors will be adjusted for in the mixed model. The secondary outcome will be categorized as binary variable for whether the patient experienced procedure related bleeding. A logistic mixed model will be utilized to analyze any difference in bleeding between procedure types adjusting for the same variables as the primary analysis. Questionnaires filled out by the provider will be compared by procedure type to evaluate ease of use and other measures from a provider standpoint.

Endpoints:

Primary: Analyze rate of “inadequate endocervical cells” reported in cytology samples obtained by using Papette and traditional spatula and cytobrush.

Secondary: Evaluate procedure related bleeding experienced by using the Papette and traditional spatula and cytobrush.

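### Devices are assigned by named unit with no randomisation described, yet patient covariates enter the primary-endpoint analysis only as a sensitivity analysis

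*Combined protocol and SAP*

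**What the plan says.** Study Design and Methods allocates the devices by place: "The Papette brush will be used to obtain Pap smear samples in women seen at CIM Ba5A, Ba5B and NW clinic". The other four units (Ba6A, Ba6B, NE and SE) use the spatula and cytobrush. The only method named is cluster sampling. No section describes random assignment, matching or stratification of units or women.

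The Data Analysis Plan sets a linear mixed model for the primary endpoint: "The model will include a fixed procedure effect and a random cluster effect". Covariates follow under a different label: "As a sensitivity analysis, covariates such as age, previous bleeding history, and other factors will be adjusted for in the mixed model". The logistic model for bleeding is described as "adjusting for the same variables as the primary analysis", although the primary model as written names no covariates.

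Some protection is present. The Data Analysis Plan states: "Descriptive statistics will be reported for patient demographics by type of procedure". Eligibility is limited to ages 21-64, and the Exclusion Criteria remove a woman who "has vaginal spotting present during cervical sampling". All seven units belong to one department. The outcome data list contains demographics and ends with this entry: "indication for pap smear, problem encountered: Provider who performed pap smear will be asked to complete a short questionnaire right after completion of exam".

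**The concern.** When nothing in the design balances the two groups on average, the estimate that carries the conclusion should account for the patient differences the study can measure. The plan treats age and bleeding history as worth adjusting for, but keeps them out of the headline result. If the women attending the three Papette units differ from those at the other four in ways that affect endocervical sampling, the primary device difference includes that case-mix difference. Recruiting more women in the same units would not reduce it.

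**Working it through.** **1. What the random effect does.** I take cluster in the model to mean the seven units; the Power Statement also uses the word for each group of 353. Device is constant within a unit, so the device effect is estimated entirely from differences between units. A random intercept charges unsystematic unit variation to the standard error. It does not shift the point estimate to correct a systematic case-mix difference between the three units and the four.

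**2. Figures taken from the plan.** The Power Statement gives 706 women, 353 per device, with "a two-sided significance level of 0.05, and an intraclass correlation was 0.1". The 353 can be reproduced with an assumed SD of 1: 2 × (1.960 + 0.842)² / 0.2² = 392.4, and 392.4 × (1 − 0.1) = 353.2. Whether that multiplier suits this design is a separate question, and nothing below depends on it. I use only 353 per arm and the ICC of 0.1.

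**3. Illustrative bias (all inputs assumed).** On the linear scale, bias = prevalence gap × effect of the factor on the inadequate rate.

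- Gap 0.20, effect 0.10: 0.20 × 0.10 = 0.020, or 2.0 points.
- Gaps of 5 to 20 points with effects of 5 to 15 points: from 0.05 × 0.05 = 0.25 point to 0.20 × 0.15 = 3.0 points.

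**4. What adjustment would remove.** Take the factor as binary, with prevalence 40% v 60% and variance 0.24 in each arm, recorded with sensitivity and specificity both equal to a. Let J = 2a − 1. Recorded gap = 0.20 × J; slope = 0.10 × 0.24 × J / variance of the recorded factor; amount removed = gap × slope.

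- a = 1: all 2.0 points removed.
- a = 0.9: gap 0.16; slope 0.10 × 0.24 × 0.8 / (0.42 × 0.58) = 0.0788; removed 1.26; residual 0.74 point.
- a = 0.8: gap 0.12; slope 0.10 × 0.24 × 0.6 / (0.44 × 0.56) = 0.0584; removed 0.70; residual 1.30 points.

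**5. Comparison with sampling error.** With 3 v 4 units, 353 per arm and v = p(1 − p), SE = √[ICC × v × (1/3 + 1/4) + (1 − ICC) × v × 2/353]. The base rate of 8.6% is 100 minus the 91.4% satisfactory rate for the Papette in the Background. It is a proxy, applied to both arms. The 5% rate and the ICC of 0.01 are assumed.

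| Base rate | ICC | SE (points) | 2.0 points ÷ SE |
|---|---|---|---|
| 8.6% | 0.1 | 7.06 | 0.28 |
| 8.6% | 0.01 | 3.00 | 0.67 |
| 5% | 0.1 | 5.49 | 0.36 |
| 5% | 0.01 | 2.33 | 0.86 |

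The 2-point bias is below one standard error in all four rows. The extreme of the range in step 3, 3.0 points, is below it at ICC 0.1, but equals 3.00 and exceeds 2.33 at ICC 0.01.

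**6. Missing covariates.** If an assumed 5% of records lacked a covariate, a complete-case model would drop 0.05 × 706 = about 35 women.

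**The case against.** The strongest reply is that adjustment of this endpoint is already planned, alongside a comparison of demographics by device. Readers would see both estimates and any measured imbalance, so the question is only which model carries the primary label. Nothing in the documents links age or indication to inadequate endocervical cells, and the bias figures are assumed throughout. This stands, and it is why the point is minor.

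A second reply concerns the remedy. Adjusting for two patient variables leaves differences between units and providers untouched, and calling that model primary could suggest more control than it gives. Indication is recorded by the provider after the exam, with the device known. The planned primary model needs only device, unit and the cytology report, whereas a complete-case adjusted model would depend on questionnaire return, which could differ by device. This also stands, so the fix needs a missing-covariate rule and a stated limitation.

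A third reply is that the bleeding model's cross-reference may show that the authors meant the primary model to be adjusted. The explicit model definition and the sensitivity label outweigh that reading. If adjustment was intended, the plan should say so.

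Two stronger readings are tempting but unsupported. A reader might infer that the plan leaves open which result prevails if the models disagree. It does not, because the labels primary and sensitivity settle it. A reader might also infer that the open-ended reference to other factors lets the headline be tuned. As written, that phrase belongs to the sensitivity model and cannot change the primary estimate.

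**Conclusion.** The point holds as a minor one. Allocation is by named unit with no randomisation described, the primary model is unadjusted, and the random effect does not make up for this because device never varies within a unit.

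The documents do not show that the primary result will be biased, and a reader should not infer that. They report no imbalance and no covariate effect. In the 2-point illustration the bias is 0.28 to 0.86 of a standard error. That rests on assumed gaps and effects, a proxy or assumed base rate, equal-sized units within each arm, and an ICC of either 0.1 (the plan's) or 0.01 (assumed). The case for the change is that it is cheap and reduces bias from measured patient factors, not that a large bias has been demonstrated.

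**What to change.** In the Data Analysis Plan:

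- Make the covariate-adjusted mixed model the primary analysis, with a closed list of pre-procedure covariates: age (from demographics or the record) and indication for the Pap smear, taken from the order or record where available.
- Add previous bleeding history only if the plan states how it is captured; the outcome data list does not name it.
- Exclude items that arise during the procedure: time of collection, ease of use, pain and problems encountered.
- State a missing-covariate rule, for example multiple imputation or a missing category for indication, so that every woman with a cytology result stays in the primary analysis and the headline does not depend on questionnaire return.
- Report the unadjusted model as the sensitivity analysis.
- Name the same covariate list in the bleeding model in place of its present cross-reference.
- State as a limitation that unit and provider differences remain unadjusted, with seven units allocated without described randomisation.

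The cost is wording, a few patient-level degrees of freedom and some handling of missing covariates. Demographics and indication are already on the outcome data list. Age is not named there but is needed for eligibility. Whether indication can be read from the order or record is not stated and should be confirmed.

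### The device is set by seven care teams or clinics, but the plan names neither the random-effect level nor a small-sample reference, and compares questionnaire items with no cluster term

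*Combined protocol and SAP*

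**What the plan says.** Study Design and Methods introduces the clustering with "Cluster sampling will be used: CIM practice in Rochester are located at Baldwin, NW, NE and SE clinics" and continues "The Baldwin practice is divided into 4 care teams: Ba5A, Ba5B, Ba6A and Ba6B". It then assigns devices, starting with "The Papette brush will be used to obtain Pap smear samples in women seen at CIM Ba5A, Ba5B and NW clinic". The other four units, two Baldwin teams and two clinics, get the comparator: "while spatula/cytobrush will be used to obtain Pap smear samples at Ba6A, Ba6B, NE and SE clinics". That makes seven units, three on one device and four on the other. The same section sets a target of 353 smears per device.

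The Power Statement says "A total sample size of 706 women (353 per cluster) is needed", and gives an intraclass correlation (ICC) of 0.1.

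In the Data Analysis Plan, the primary outcome gets a linear mixed model: "The model will include a fixed procedure effect and a random cluster effect". For bleeding, "A logistic mixed model will be utilized to analyze any difference in bleeding between procedure types". Neither model has a stated level for the random effect, degrees-of-freedom method or reference distribution. The remaining provider items get one sentence: "Questionnaires filled out by the provider will be compared by procedure type to evaluate ease of use and other measures from a provider standpoint". Ease, time and pain belong to Aim 3, and problems encountered is in the Methods list of questionnaire items. None of the four is a listed endpoint.

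**The concern.** Every woman in a given team or clinic gets the same device, so a difference between devices can be judged only against differences between units. There are seven of these, however many women are sampled. The plan partly recognises this by choosing mixed models, but leaves three gaps.

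- **Level of the random effect.** The word cluster is never tied to the seven units, and the Power Statement uses it for a whole arm. Taken literally, that gives one cluster per device, and a random effect at that level cannot be separated from the device effect.
- **Reference distribution.** With seven units, a normal and a t reference give materially different intervals and p-values. The result would depend on a software default that nobody has recorded.
- **Questionnaire items.** A comparison by device with no unit term can present ordinary differences between care teams as differences between devices.

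**Working it through.** **Inputs from the documents.** Seven units, 3 versus 4, and 353 women per device (Methods); two-sided 0.05, 80% power, mean difference 0.2 and ICC 0.1 (Power Statement); 91.4% satisfactory samples reported for the Papette (Background).

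**Assumptions.** SD = 1, so that 0.2 means 0.2 SD. The inadequate rate is 100 - 91.4 = 8.6%, although a satisfactory sample may not be the exact complement of inadequate endocervical cells; 20% is a sensitivity value. Unit sizes are 118, 118, 117 versus 89, 88, 88, 88 (even) or 190, 110, 53 versus 160, 100, 60, 33 (uneven). ICCs other than 0.1 are illustrative.

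**1. The plan's own figure.** 2 × (1.960 + 0.842)² / 0.2² = 392.4 per device. Multiplying by (1 - 0.1) gives 353.2 per device, or 706.4 in total, which matches 706. So 353 is a number per device. The factor (1 - ICC) suits allocation of women to device within clusters, not whole units on one device.

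**2. Degrees of freedom.** 7 units - 2 device means = 5. The two-sided 5% critical value is 2.571 rather than 1.960, and a 1.960 cut-off applied to t with 5 df has a true error of 10.7%.

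**3. Primary model.** Beta-binomial data with no device effect, linear random-intercept model for the seven units, REML, even sizes, 20,000 runs per cell. Type I error with a normal reference:

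| ICC | 0.005 | 0.01 | 0.02 | 0.05 | 0.1 |
|---|---|---|---|---|---|
| rate 8.6% | 6.4% | 7.9% | 9.0% | 10.0% | 8.9% |
| rate 20% | 6.9% | 8.3% | 9.9% | 10.7% | 10.5% |

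Uneven sizes give 7.1-11.6%. The same model with a 5-df t reference gives 1.8-5.1% (even) and 2.2-5.4% (uneven). A 5-df t-test on the seven unit proportions gives 3.9-5.1%.

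**4. Bleeding.** A smaller simulation of the logistic mixed model (1,500 runs per setting, rates 10-30%) gave 7.9-15.9% with a normal reference and 1.5-8.0% with 5-df t. The t reference is therefore only a partial cure there.

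**5. Questionnaire items tested without a unit term.** In SD units, the true variance of the device difference is ICC × (1/3 + 1/4) + (1 - ICC) × 2/353. An unclustered test uses 2/353 = 0.00567. The ratio of the two is the design effect DE, and the error is 2 × [1 - Φ(1.96/√DE)].

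| ICC | True variance | DE | Error |
|---|---|---|---|
| 0.005 | 0.00292 + 0.00564 = 0.00855 | 1.51 | 11% |
| 0.01 | 0.00583 + 0.00561 = 0.01144 | 2.02 | 17% |
| 0.1 | 0.05833 + 0.00510 = 0.06343 | 11.2 | 56% |

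Uneven sizes raise these errors to 12.6%, 19.5% and 59.8%. A 5-df t-test on unit means held 5.0-5.5% for a 5-point item and 4.6-5.2% for a skewed time (6,000 runs).

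**6. Power.** At ICC 0.1 the standard error is √0.06343 = 0.252, so the noncentrality is 0.2/0.252 = 0.79, and power on t with 5 df is about 10%. At ICC 0.005 the standard error is 0.0925 and power is about 42%.

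**The case against.** The strongest reply is that the Methods already make the meaning clear. The sentences run from cluster sampling, through the sites and Baldwin's division into teams, to a device for each of seven named units. The natural reading is that these are the clusters, and 353 per cluster is a slip for 353 per device. That stands. A reader might infer instead that the four locations are the clusters, since they come first after the word; simulated error on that reading reaches 54-57% at ICC 0.1. The documents do not support it, because Baldwin would then hold both devices, and that figure carries no weight here.

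Second, the plan never says that a normal reference will be used. That is true, so the 6-11% is conditional. At low ICC with even sizes the excess is also modest, at 6-8%.

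Third, a reader might infer that the Papette will be wrongly declared non-inferior at these rates. The hypothesis is one of non-inferiority, but no margin is stated and the power calculation is for a two-sided difference. The rates above are two-sided errors for a test of no difference and cannot be read as false non-inferiority claims.

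Fourth, comparing questionnaires need not mean testing them, and the items are not listed endpoints. The sentence on chi-square and Kruskal-Wallis tests might be meant to cover them. However, it follows directly on patient demographics, and if it did apply it would ignore the clustering, which is the problem described.

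**Conclusion.** The point holds as a specification gap with a real effect on error rates. The design gives about 5 df for any device contrast. The plan does not tie its random effect to the seven units, misuses the word cluster in the Power Statement, states no small-sample reference, and gives the questionnaire items no cluster term.

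The size is conditional. A normal reference on the seven-unit linear model gives about 6-11% in place of 5%, and about 9% at the plan's ICC of 0.1 with an 8.6% rate. Unclustered tests of questionnaire items give about 11%, 17% and 56% at ICC 0.005, 0.01 and 0.1. Unit sizes and event rate are assumed, and all variation is placed at the level of the seven units.

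It does not follow that the planned mixed models are unsuitable. With the seven units as the random effect and 5 df, the linear model keeps the primary error at or close to 5% or below. Making a unit-level t-test the main analysis instead would be a matter of preference.

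**What to change.** - State in the Data Analysis Plan that the random cluster effect is the seven care teams/clinics, for both mixed models.
- In the Power Statement, change 353 per cluster to 353 per device.
- Keep the planned mixed models, with REML for the linear one, and refer the device effect to t with 5 df.
- Add a 5-df t-test on the seven unit-level proportions as a check, above all for bleeding, where 5 df only partly corrects the logistic model.
- For ease, time, pain and problems, specify a unit-level comparison or a random unit effect, or report them descriptively without p-values. Label them exploratory in either case.

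The change is to wording only and needs no new patients or data. Intervals from the linear model become 2.571/1.960 = 1.31 times as wide as those with a normal reference. At an 8.6% rate with even units, the half-width goes from 5.1 to 5.13 × 1.312 = 6.7 percentage points at ICC 0.005, and from 12.5 to 12.54 × 1.312 = 16.5 at ICC 0.1. At small ICC the 5-df reference is conservative, with type I error of about 2%. The low power from seven units, about 10% for 0.2 SD at ICC 0.1, is not repaired by any of this.
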